### **8.7. Population Pharmacokinetic Analysis**

The PPK and E-R analyses will be performed based on modeling analysis plan (MAP) and reported separately from the final clinical study report. The MAP will be submitted to the Food and Drug Administration (FDA) prior to unblinding subject data for analysis.

### **8.8. Statistical Analysis Plan**

A detailed SAP will be signed and submitted to the FDA prior to database lock.

### **8.9. Interim Analysis**

No formal interim analysis is planned. The DMC will be responsible for closely reviewing the unblinded safety data and for providing their recommendations. The detailed objectives and procedures will be described in the DMC Charter.

## APPENDIX 1. SCHEDULE OF ASSESSMENTS

Schedule of Assessments																		
Study Period	Screen	Treatment Period																FU a
Visit # (V)	V1	Baseline V2	V3	V4-6 a	V7	V8-10 a	V11	V12-14 a	V15	V16-18 a	V19	V20-22 a	V23	V24	V25	EOT/ ET b V26	EOS FU c V27	
Week (W)	W -6	W0	W2	W3-5	W6	W7-9	W10	W11-13	W14	W15-17	W18	W19-21	W22	W26	W30	W34	W38	
Study Day (D) [Window based on Day 1 Visit]	D -42 to -1	D1	D15 [±3]	D22, D29, & D36 [±3]	D43 [±3]	D50, D57, & D64 [±3]	D71 [±3]	D78, D85, & D92 [±3]	D99 [±3]	D106, D113, & D120 [±3]	D127 [±3]	D134, D141, & D148 [±3]	D155 [±3]	D183 [±3]	D211 [±3]	D238 [±3]	295 [±7]	
Informed consent	X																	
Inclusion/ exclusion criteria	X																	
Demographic information	X																	
Medical history	X																	
Prior medications d	X																	
Physical examination e	X	X	X		X		X		X		X		X	X	X	X		
Height and weight f	X	X															X	
Vital signs (blood pressure [sitting], heart rate, respiration rate, and body temperature) g	X	X	X		X		X		X		X		X	X	X	X		
Heart rhythm monitoring (wearable) h	X	X	X		X		X		X		X		X	X	X			

Schedule of Assessments																		
Study Period	Screen	Treatment Period																📞 FU a
Visit # (V)	V1	Baseline V2	V3	📞 V4-6 a	V7	📞 V8-10 a	V11	📞 V12-14 a	V15	📞 V16-18 a	V19	📞 V20-22 a	V23	V24	V25	EOT/ ET b V26	EOS FU c V27	
Week (W)	W -6	W0	W2	W3-5	W6	W7-9	W10	W11-13	W14	W15-17	W18	W19-21	W22	W26	W30	W34	W38	
Study Day (D) [Window based on Day 1 Visit]	D -42 to -1	D1 [±3]	D15 [±3]	D22, D29, & D36 [±3]	D43 [±3]	D50, D57, & D64 [±3]	D71 [±3]	D78, D85, & D92 [±3]	D99 [±3]	D106, D113, & D120 [±3]	D127 [±3]	D134, D141, & D148 [±3]	D155 [±3]	D183 [±3]	D211 [±3]	D238 [±3]	295 [±7]	
12-lead ECG i	X	X	X		X		X		X		X		X	X	X	X		
Chest X-ray	X																	
FDG-PET CT scan j	X						X (Cohort B only)						X (Cohort A only)			X		
ECHO	X						X						X			X		
Pulmonary function tests (FEV1, FEV1/FVC, and FVC)		X					X						X				X	
PROs (KSQ, FAS, and SGA)		X					X						X			X		
mGTI		X					X						X			X		
Recording of steroid dose and rescue therapy use k		X	X	X	X	X	X	X	X	X	X	X	X	X	X	X		
Concomitant medication/concurrent procedures l		X	X	X	X	X	X	X	X	X	X	X	X	X	X	X	X	
Serious adverse event monitoring m	X	X	X	X	X	X	X	X	X	X	X	X	X	X	X	X	X	

Schedule of Assessments																		
Study Period	Screen	Treatment Period																📞 FU a
Visit # (V)	V1	Baseline V2	V3	📞 V4-6 a	V7	📞 V8-10 a	V11	📞 V12-14 a	V15	📞 V16-18 a	V19	📞 V20-22 a	V23	V24	V25	EOT/ ET b V26	EOS FU c V27	
Week (W)	W -6	W0	W2	W3-5	W6	W7-9	W10	W11-13	W14	W15-17	W18	W19-21	W22	W26	W30	W34	W38	
Study Day (D) [Window based on Day 1 Visit]	D -42 to -1	D1	D15 [±3]	D22, D29, & D36 [±3]	D43 [±3]	D50, D57, & D64 [±3]	D71 [±3]	D78, D85, & D92 [±3]	D99 [±3]	D106, D113, & D120 [±3]	D127 [±3]	D134, D141, & D148 [±3]	D155 [±3]	D183 [±3]	D211 [±3]	D238 [±3]	295 [±7]	
Adverse event monitoring m		X	X	X	X	X	X	X	X	X	X	X	X	X	X	X	X	
TB test	X																	
Viral screen (Hep B, Hep C, HIV)	X																	
FSH (women only & if indicated) n	X																	
Sample for anti GM-CSF autoAb q	X																	
Sample for ADA (antibodies to namilumab) o		X								X							X	
Cytokine and chemokine samples		X					X		X					X		X		
Samples for hsCRP, SAA, sarcoid biomarkers, and SP-D measurement		X					X		X					X		X		

Schedule of Assessments																		
Study Period	Screen	Treatment Period																FU a
		Baseline	V2	V3	V4-6 a	V7	V8-10 a	V11	V12-14 a	V15	V16-18 a	V19	V20-22 a	V23	V24	V25	EOT/ ET b	EOS FU c
Visit # (V)	V1	V2	V3	V4-6 a	V7	V8-10 a	V11	V12-14 a	V15	V16-18 a	V19	V20-22 a	V23	V24	V25	V26	V27	
Week (W)	W -6	W0	W2	W3-5	W6	W7-9	W10	W11-13	W14	W15-17	W18	W19-21	W22	W26	W30	W34	W38	
Study Day (D) [Window based on Day 1 Visit]	D -42 to -1	D1	D15 [±3]	D22, D29, & D36 [±3]	D43 [±3]	D50, D57, & D64 [±3]	D71 [±3]	D78, D85, & D92 [±3]	D99 [±3]	D106, D113, & D120 [±3]	D127 [±3]	D134, D141, & D148 [±3]	D155 [±3]	D183 [±3]	D211 [±3]	D238 [±3]	295 [±7]	
Clinical laboratory: hematology	X	X	X		X		X		X		X		X	X	X	X		
Clinical laboratory: blood chemistry	X	X	X		X		X		X		X		X	X	X	X		
Clinical laboratory: urinalysis	X	X	X		X		X		X		X		X	X	X	X		
HbA 1C		X					X							X			X	
Vitamin D		X					X							X			X	
NT-proBNP		X					X							X			X	
Troponin		X					X							X			X	
Urine pregnancy test β-hCG (WCBP only)	X	X					X							X			X	
PK sample p			X		X				X					X		X		
Randomization and/or treatment assignment		X																
Administration of study drug		X	X		X		X		X		X		X	X	X			

Abbreviations: β-hCG = beta human chorionic gonadotropin, ADA = anti-drug antibodies, CT = computed tomography, ECG = electrocardiogram, ECHO = echocardiogram, EOS = End-of-Study, EOT = End-of-Treatment, ET = early termination, FAS = Fatigue Assessment Scale, FDG = fluorodeoxyglucose, FSH = follicle-stimulating hormone, FU = Follow-up Visit, GM-CSF autoAb = granulocyte macrophage colony-stimulating factor autoantibody, HbA1C = glycosylated hemoglobin, Hep = hepatitis, HIV = human immunodeficiency virus, hsCRP = high-sensitivity C-reactive protein, KSQ = King's Sarcoidosis Questionnaire, mGTI = modified glucocorticoid toxicity index,

NT-proBNP = N-terminal (NT)-proB-type natriuretic peptide, PET = positron emission tomography, PK = pharmacokinetic, PRO = patient-reported outcome, SAA = serum amyloid A, SGA = Subject Global Assessment, SP-D = serum surfactant protein D, TB = tuberculosis, WCBP = woman of childbearing potential.

- a. The Investigator will conduct weekly FU (via phone, telemed, or any site-approved remote method).
- b. Subjects who withdraw or are withdrawn from the study early will undergo all Week 34 ET/EOT Visit procedures whenever possible.
- c. The FU will be a phone call approximately 8 weeks (56 days) following the last dose of study drug.
- d. Collect medication history from the 6 months leading up to, and including, the time of the Screening Visit, including prescription medications, over-the-counter medications, and herbal supplements/vitamins.
- e. A full physical examination will be performed at Screening and the EOT/ET Visit; an abbreviated targeted physical examination will be performed at all other clinic Visits.
- f. Height will be measured at Screening only; weight will be measured at all indicated timepoints.
- g. Vital signs will be assessed at all timepoints specified above. On study drug administration days, vital signs will be assessed predose (within 15 minutes) and  $\pm 30$  minutes post-dose.
- h. Subjects will be monitored via ePatch for 10 consecutive days; one patch will be worn for 5 days, then the patch will be replaced by the subject, and the second patch will be worn for an additional 5 days.
- i. A single 12-lead standard ECG will be recorded at all timepoints specified above.
- j. Only central imaging interpretation will be accepted for eligibility determination. Scans conducted as part of the usual clinical management of the subject within 2 weeks prior to informed consent may be considered/assessed for use in place of the Screening PET/CT scan if the scans can be uploaded to central imaging vendor for central read and the OCS dose has not changed in the 4 weeks prior to the scan. Refer to [Section 7.1.2.1](#) for details
- k. Document whether the patient has completed taper by the specified timepoints described in [Appendix 8](#) or whether a dose increase/maintenance was needed. See [Section 6.4](#) for more details regarding rescue therapy. Patients should record OCS dose daily on provided eDiary.
- l. Collect information on concomitant medications and concurrent procedures from the time of informed consent through the EOS Visit, including prescription medications, over-the-counter medications, and herbal supplements/vitamins. All medications and procedures prior to randomization should be listed in the subject's medical history.
- m. All serious adverse events will be monitored and collected from the time of informed consent through the 8 weeks (56 day) post last dose of study drug FU. All adverse events will be monitored and collected from the time of randomization through the 8 weeks (56 day) post last dose of study drug FU. Treatment-emergent adverse events will be those that start or change in severity after the first dose of study drug.
- n. If necessary, follicle-stimulating hormone will be measured at Screening to confirm postmenopausal status.
- o. The ADA samples will be collected at Baseline (prior to the first dose) of Day 1 (Week 0), at Week 14, and at EOT. For subjects who terminate the study early, one ADA sample will be collected before discharging, when possible. Actual sampling time will be recorded.
- p. The PK samples will be collected prior to study drug administration at the appropriate timepoints and actual sampling time will be recorded.
- q. Investigators in the state of New York will remain blinded to the anti-GMCSF auto-antibody assay results until the end of the trial due to regulations within the state of New York.

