Treatment and Study Duration	
Participation will be approximately 44 weeks (308 days) as follows:
 

• Up to 6-week (42 days) Screening Period;

• 34-week (238 days) Treatment Period (with steroid tapering during the first 22 weeks for subjects participating in Cohort A);

• Follow-up phone call approximately 4 weeks (28 days) after the End-of-Treatment (EOT) Visit (approximately 8 weeks [56 days] after the last dose of study drug at Week 30).

Study Endpoint(s)	
Primary Endpoints: The primary endpoint of this study includes the following:
 

• Incidence and severity of TEAEs, SAEs, and adverse events (AEs) leading to discontinuation.

 
Secondary Endpoints:
 

• Other safety endpoints including:

○ Incidence and magnitude of treatment-emergent laboratory abnormalities;

○ Change from baseline in vital signs;

○ Change from baseline in electrocardiogram (ECG) parameters.

	

• Mean change from baseline in PET maximum standardized update value (SUVmax), SUVmean, and total glycosylation;

• Cumulative arrhythmia burden and hospitalization for cardiac events;

• Mean change from baseline in left ventricular ejection fraction (LVEF) and global longitudinal strain (GLS) on transthoracic echocardiogram (TTE);

• Cumulative oral steroid use, modified glucocorticoid toxicity index (mGTI), and mean change from Baseline in glycosylated hemoglobin (HbA1C);

• Proportion of subjects requiring rescue therapy (either cohort) and proportion of subjects successfully achieving steroid taper without requiring rescue therapy (Cohort A);

• Mean change from baseline in KSQ (General and sub-domains), Fatigue Assessment Scale (FAS), and Subject Global Assessment (SGA);

• Assessments of PPK and E-R relationships for safety and efficacy if data permit.

 
Note: For endpoints defined as mean change from baseline, the primary assessment will be at Week 34.

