### **3. INVESTIGATION PLAN**

#### **3.1. Overall Study Design and Plan Description**

This is a Phase 2a, 2-cohort study including a randomized, double-blind, placebo-controlled cohort (Cohort A), and an open-label cohort (Cohort B) assessing the safety and tolerability of namilumab in subjects with active CS.

[figure not shown]
Approximately 30 total subjects are planned for this study. Cohort A will include 20 subjects. Cohort B is open-label and will include 10 subjects.

Participation will be approximately 44 weeks (308 days) as follows:

- Up to 6-week (42 days) Screening Period;
- 34-week (238 days) Treatment Period (with steroid tapering during the first 22 weeks for subjects participating in Cohort A);
- Follow-up phone call approximately 4 weeks (28 days) after the End-of Treatment (EOT) Visit (approximately 8 weeks [56 days] after the last dose of study drug at Week 30).

The study design is presented in [Figure 1](#).

Figure 1. Study Design

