### **3.1.3. Follow-up Period**

All subjects will have a contact (telephone call) approximately 8 weeks (56 days) after the last dose of study drug to obtain information on concomitant medication use and SAEs or any AEs that were ongoing at the time of the EOT/Early Termination (ET) Visit. See the SOA ([Appendix 1](#)) for details on what assessments are required.

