#### **4.4.2.3. Participant Discontinuation/Withdrawal of Consent**

Subjects may withdraw from the study at any time, for any reason, and may leave the study without specifying a reason at his/her own request. Additionally, subjects may request destruction of any samples taken and not tested, and the Investigator must document this in the site study records.

The Investigator should make all efforts to obtain information about possible underlying AEs leading to the decision to withdraw from study participation. Any AE or SAE information elicited must be documented in the subject's source documents and the eCRF. Refer to the SOA ([Appendix 1](#)) for data to be collected at the time of study discontinuation and follow-up and for any further evaluations that need to be completed.

Unless the subject who prematurely discontinues trial participation, specifically withdraws consent for any follow-up contact, all subjects will continue to be contacted at the same visit interval through the end of the study to obtain their health status. Investigators and site staff should encourage subjects to allow as much follow-up as possible and will need to clearly identify and document in writing as to which of the following options the subject has chosen.

- The subject has withdrawn from further treatment with study drug but will agree to continue with study visits and study assessments through the end of the Double-blind Treatment Period.
- The subject has withdrawn from further treatment with study drug, will not agree to continue with study visits and study assessments, but will agree to phone call assessments in accordance with the visit schedule.
- The subject is not willing to be contacted in accordance with the visit schedule but will allow the Investigator access to their medical records and EOS contact.

- The subject is not willing to allow any direct contact, access to medical records, or contact with care provider. In this case, public records may be used to confirm vital status at the end of the study.

For the purpose of this protocol, only subjects who are not willing to allow any direct contact, access to medical records, or contact with care provider will be deemed as subjects who have withdrawn consent.

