## 7.3. Adverse and Serious Events

### 7.3.1. Adverse Events

AE definitions and assignment of severity and causality are detailed in [Appendix 3](#).

Non-serious AE collection will be initiated after the subject has been randomized/enrolled and continue to be collected through the follow up phone call visit.

Any sign, symptom, or illness occurring prior to first dose of double-blind study drug will be captured in the medical history. TEAEs are defined as any AE reported after the first dose of study drug and continue to be collected through the follow up phone call visit. AE definitions and assignment of severity and causality are detailed in [Appendix 3](#).

AEs will be elicited from the subject (or, when appropriate, from a caregiver, delegate, or the subject's legally authorized representative) by the study site staff using a non-leading question such as "How are you feeling today?" or "Have you had any health concerns since your last visit?"

The Investigator and any designees are responsible for detecting, documenting, and reporting events that meet the definition of an AE or SAE and remain responsible for following up AEs that are serious, considered related to the study drug or the study, or that caused the subject to discontinue the study drug (see [Section 4.4.2](#)).

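### The schedule dates the final follow-up call Day 295, 84 days after the last dose, where the rest of the protocol gives 56 days (about Day 267); TEAE is also worded four ways

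*Combined protocol and SAP*

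**What the plan says.** **Date of the final call.** Footnote c of Appendix 1 reads: "The FU will be a phone call approximately 8 weeks (56 days) following the last dose of study drug". Section 3.1 places the call "approximately 8 weeks [56 days] after the last dose of study drug at Week 30", and the synopsis describes it as a "Follow-up phone call approximately 4 weeks (28 days) after the End-of-Treatment (EOT) Visit". Section 3.1.3 repeats the 56 days. The synopsis and Section 3.1 both give total participation as 308 days. In the Schedule of Assessments the call is visit V27, labelled W38. Its Study Day entry is 295 ±7 in all four printings of the header, and that row is headed "Window based on Day 1 Visit".

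**End of adverse event collection.** Section 7.3.1 says of non-serious events that "AE collection will be initiated after the subject has been randomized/enrolled and continue to be collected through the follow up phone call visit". Appendix 3 ends the active phase of the study at the follow-up visit. The opening of Appendix 3 (AEs) and Section 7.3.2 (SAEs) instead end reporting 56 days after the last dose. Footnote m runs collection to a follow-up contact that it describes as 56 days after the last dose.

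**TEAE definition.** There are four texts:
- Section 7.3.1: "TEAEs are defined as any AE reported after the first dose of study drug".
- Section 8.6: newly appearing, or worsening in severity, from the start of active treatment.
- Footnote m: starting, or changing in severity, after the first dose.
- Appendix 3: new and not part of the chronic history, or increased in severity or frequency during the active phase, which starts at the first dose.

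**The concern.** The primary endpoint is the incidence and severity of TEAEs, SAEs and AEs leading to discontinuation. Its observation period needs one end and its events need one definition. The plan ties the end of TEAE collection to a call, then gives that call two dates four weeks apart. Section 7 tells sites that timing is set out in the Schedule of Assessments and that adherence to it is required, so the printed day may be used to book calls. A site that books from the Study Day row and a site that follows footnote c would observe their subjects for different lengths of time.

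The reference point also differs. The row counts from Day 1 and footnote c counts from the last dose. For a subject who completes dosing on schedule the two should agree once the date is right. They cannot agree for a subject who stops study drug early but, as Section 4.4.2.3 provides, "will agree to continue with study visits and study assessments through the end of the Double-blind Treatment Period".

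The four TEAE texts add a separate uncertainty about which events belong to the endpoint.

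**Working it through.** **Inputs from Appendix 1.** Week 30 (last dose) is Day 211 ±3; Week 34 (EOT) is Day 238 ±3; Week 38 (call) is Day 295 ±7. The intervals from the text are 56 days after the last dose, 28 days after EOT, and 308 days in total.

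**The row's own numbering.** Study Day = 7 × week + 1. This reproduces 24 of the 26 days listed from W0 to W38. The exceptions are:
- W34: 7 × 34 + 1 = 239 against 238 printed, one day off and inside the ±3 window.
- W38: 7 × 38 + 1 = 267 against 295 printed, 28 days off.

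**Can the stated intervals give 295?**
- From the last dose: 211 + 56 = 267.
- From EOT: 238 + 28 = 266, or 239 + 28 = 267.
- Total participation: 42 + 238 + 28 = 308, as stated. A call on Day 295 gives 42 + 294 = 336.

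None gives 295. Working back from 295:
- (295 − 1) / 7 = Week 42.
- 295 − 211 = 84 days after the last dose.
- 295 − 238 = 57 days after EOT, against 28 stated.
- 239 + 56 = 295, so the 56 days may have been counted from Week 34 instead of from the last dose. That is an inference about the cause; the contradiction does not depend on it.

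**Do the windows close the gap?**
- Counted from Day 1: 267 ±7 is Days 260-274 and 295 ±7 is Days 288-302. The gap is 288 − 274 = 14 days.
- Counted from the actual dose (Days 208-214): a call 56 ±7 days later falls between 208 + 49 = 257 and 214 + 63 = 277. The gap is still 288 − 277 = 11 days.
- The printed window therefore means 288 − 214 = 74 to 302 − 208 = 94 days after the last dose.

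**TEAE texts side by side.**

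| Source | Change that qualifies | Start |
|---|---|---|
| 7.3.1 | any AE reported | first dose of study drug |
| 8.6 | new, or worse in severity | active treatment |
| Footnote m | new, or any change in severity | first dose of study drug |
| Appendix 3 | new, or increase in severity or frequency | first dose of study drug |

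They disagree on three points: whether a change includes improvement, whether frequency counts, and whether the start is the first dose of study drug or active treatment, a term that is unclear for the placebo arm. The end also varies. Section 7.3.1 and Appendix 3 end at the call, while the definitions in Section 8.6 and footnote m state no end of their own.

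**The case against.** The strongest reply is that the intended date can be recovered from the same column. W38 stands above it, footnote c is attached to it, and the synopsis and Sections 3.1 and 3.1.3 agree. Footnote m and the opening of Appendix 3 also tie the end of collection to 56 days after the last dose, so only Section 7.3.1 and the active-phase sentence move with the call. A late call still covers the 56 days, later onsets can be removed by date, and safety is analysed descriptively. All of this stands and limits the consequence. It does not reconcile the operative schedule with the text.

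On TEAEs, Section 7.3.1 sends anything before the first dose to medical history and refers to Appendix 3 for what an AE is. Appendix 3 counts clinically significant worsening and recurrence of a pre-existing condition as AEs. A condition that merely eases would rarely be an AE at all, and one that becomes more frequent would often be recorded as a recurrence. Section 8.6 also leaves full details to the SAP, which is not part of the text examined here. This narrows the practical difference considerably, but the wordings still conflict.

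Three stronger readings are tempting and are not supported:
- A reader might infer that SAE reporting would already have closed while non-serious AEs were still being collected. Section 7.3.2 read alone suggests it, but the schedule marks SAE monitoring at V27, and the follow-up paragraph of Appendix 3 covers serious and non-serious events that develop before the final call.
- A reader might infer that subjects who stop drug early are left unobserved. Section 4.4.2.3 keeps them in contact at the same visit interval unless they refuse it. What remains is where their collection period ends, and that question would persist with the date corrected.
- A reader might infer bias between arms or a known change in TEAE counts. Nothing in the documents shows either.

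**Conclusion.** The point holds as an internal contradiction. Day 295 conflicts with its own column label, footnote c, the synopsis, Sections 3.1 and 3.1.3, and the 308-day total. The difference is 28 days, and the visit windows do not absorb it. A site scheduling from the row would extend TEAE collection by about 28 days beyond the 56-day limit. This assumes a Week 30 last dose on or near Day 211 and reads the approximate interval as no looser than the printed ±7 days.

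The four TEAE wordings are a separate, smaller defect. They need to be made one because they feed the primary endpoint, although the AE definition in Appendix 3 removes much of the practical difference. The effect on counts is not quantified. Both items should be fixed; neither threatens the validity of the trial.

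**What to change.** - Reconcile the V27 study day with the W38 label and the 56-day text in all four schedule headers. By the document's own arithmetic this is Day 267.
- State that the V27 window and the end of AE and TEAE collection are both counted from the last dose, including for subjects who stop study drug early but stay in visits.
- Adopt one TEAE definition with one start (first dose of study drug, namilumab or placebo) and one end. Use it in Section 7.3.1, Section 8.6, footnote m, Appendix 3 and the SAP, and say explicitly whether improvement and increased frequency count.

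The cost is one date repeated four times, plus wording in those places. No visit or sample is added. If frequency is kept, check that the AE record captures it, because the assessment items in Appendix 3 cover severity, relationship and action taken only.
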